6.2 Exclusion Criteria

Subjects in both phase 1b and 2 are excluded from the study if any of the following criteria apply.

201 Subject is concurrently receiving treatment with calcineurin-inhibitor plus sirolimus (either agent alone is acceptable).

202 Subject has received ibrutinib, imatinib, bortezomib, entospletinib, ruxolitinib or other JAK inhibitor, or treatment with any investigational drug or device within 4 weeks prior to starting efavaleukin alfa.

203 Subject has received treatment with T-cell depleting, B-cell depleting or IL-2 signaling targeted medication (eg, ATG, alemtuzumab, basiliximab, denileukin diftitox, IL-2, rituximab) within 12 weeks prior to starting efavaleukin alfa.

204 Subject has received treatment with T regulatory cell expanding therapies (ie, PUVA, UVB, adoptively transferred T regulatory cells) within 4 weeks prior to starting efavaleukin alfa.

205 Subject has received a donor lymphocyte infusion within 12 weeks prior to starting dose of efavaleukin alfa.

206 Subject with active morphologic relapse/progression of hematologic malignancy post transplantation. Persistent CLL early after transplantation that subsequently entered remission will not be excluded.

207 Subject has a history of malignancy, other than the indication for hematopoietic cell transplantation, with the following exceptions:

- adequately treated nonmelanoma skin cancers without current evidence of disease
- adequately treated cervical carcinoma in situ without current evidence of disease
- adequately treated breast ductal cancer in situ without current evidence of disease

- any malignancy treated with curative intent and with no evidence of active disease present for more than 5 years prior to screening and felt to be at low risk for recurrence by the treating physician

208 Subject has a history of thrombotic microangiopathy, hemolytic-uremic syndrome or thrombotic thrombocytopenic purpura.

209 Subject has an active infection requiring treatment with intravenous antibiotics or has been hospitalized for treatment of an active infection in the 4 weeks prior to starting dose of efavaleukin alfa.

210 Subject has known history of active tuberculosis.

211 Positive test for tuberculosis during screening defined as either:

- positive purified derivative (PPD) (\geq 5 mm of induration at 48 to 72 hours after test is placed) OR
- positive Quantiferon or T-SPOT test
 - a positive PPD and a history of Bacillus Calmette-Guérin vaccination are allowed with a negative Quantiferon or T-SPOT test and negative chest x-ray
 - a positive PPD test (without a history of Bacillus Calmette-Guérin vaccination) or a positive Quantiferon or T-SPOT test are allowed if they have ALL of the following at screening:
 - no symptoms per tuberculosis worksheet provided by Amgen
 - document history of a completed course of adequate prophylaxis (completed treatment for latent tuberculosis per local standard of care prior to the start of investigational product)
 - no known exposure to a case of active tuberculosis after most recent prophylaxis
 - negative chest X-ray
 - an indeterminate Quantiferon or T-SPOT test is allowed if they have ALL of the following at screening:
 - no symptoms per tuberculosis worksheet provided by Amgen
 - no known recent exposure to a case of active tuberculosis
 - no history of a positive Quantiferon or T-SPOT test without documented history of a completed course of adequate prophylaxis (completed treatment for latent tuberculosis per local standard of care prior to the start of investigational product)
 - negative chest X-ray
 - are deemed to be at low risk for tuberculosis exposure in the opinion of the principle investigator

212 Subject is positive for hepatitis B surface antigen, hepatitis B core antibody (confirmed by hepatitis B deoxyribonucleic acid [DNA] polymerase chain reaction [PCR] test) or detectable hepatitis C virus ribonucleic acid (RNA) by PCR (screening is generally done by hepatitis C antibody [HepCAb], followed by hepatitis C virus RNA by PCR if HepCAb is positive). Subjects with a history of hepatitis B vaccination without history of hepatitis B are allowed.

- 213 Subject has positive test results for Human Immunodeficiency Virus (HIV) or known to be HIV-positive.
- 214 Phase 1b subject has a drug or alcohol urine test positive for illicit drugs at the screening visit. Medications detected by the drug test are allowed if they are being taken under the direction of a physician or if permitted for recreational purposes as per country regulations.
- 215 Phase 1b subject cannot be a current smoker, nor have used any nicotine or tobacco containing products within the last 6 months prior to screening. These types of products include but are not limited to: snuff, chewing tobacco, cigars, cigarettes, pipes, or nicotine patches.
- 216 Phase 1b subject is unable to avoid alcohol during the 4-week DLT evaluation period or tobacco consumption for the duration of the study.
- 217 Subject has known sensitivity to efavaleukin alfa or its excipients to be administered during dosing.
- 218 Subject likely to be unable to complete all protocol-required study visits or procedures, and/or to comply with all required study procedures (eg, Clinical Outcome Assessments [COAs]) to the best of the subject and investigator's knowledge.
- 219 History or evidence of any other clinically significant disorder, condition, or disease (with the exception of those outlined above) that, in the opinion of the investigator or Amgen physician, if consulted, would pose a risk to subject safety or interfere with the study evaluation, procedures, or completion.
- 220 Females who are pregnant or breastfeeding, or planning to become pregnant or breastfeed during treatment and for an additional 6 weeks after the last dose of efavaleukin alfa.
- 221 Females of child-bearing potential with a positive pregnancy test (assessed by a serum pregnancy test at screening and a urine pregnancy test at baseline).
- 222 Females of childbearing potential who are unwilling to use 1 highly effective method of contraception during treatment and for an additional 6 weeks after receiving the last dose of efavaleukin alfa. Refer to [Appendix 5](#) for additional contraception information.
- 223 Subject has previously entered this study.

6.3 Lifestyle Restrictions

6.3.1 Alcohol and Tobacco (Phase 1b)

Phase 1b subjects will be required to avoid alcohol consumption during the 4-week DLT evaluation period. After the 4-week DLT evaluation period, alcohol consumption is strongly discouraged and is prohibited in those subjects with hepatic GVHD, underlying hepatic abnormalities, or elevated liver function tests at the baseline visit.

Phase 1b subjects must not use any nicotine or tobacco containing products within 6 months prior to screening and throughout the study. These types of products include but are not limited to: snuff, chewing tobacco, cigars, cigarettes, pipes, or nicotine patches.

6.4 Subject Enrollment

Before subjects begin participation in any study-specific activities/procedures, Amgen requires a copy of the site's written institutional review board/independent ethics committee (IRB/IEC) approval of the protocol, informed consent form, and all other subject information and/or recruitment material, if applicable (see [Appendix 3](#)).

The subject must personally sign and date the IRB/IEC and Amgen approved informed consent before commencement of study-specific procedures.

A subject is considered enrolled when the investigator decides that the subject has met all eligibility criteria and has been enrolled via the Interactive Voice Response System/Interactive Web Response System (IVRS/IWRS). The investigator is to document this decision and date, in the subject's medical record and it will be transferred from the IVRS/IWRS to the subject's enrollment case report form (CRF).

Subjects will be screened to determine eligibility 28 days prior to baseline visit (see [Table 2-1](#) and [Table 2-7](#)).

Each subject who enters into the screening period for the study receives a unique subject identification number before any study-related activities/procedures are performed. The subject identification number will be assigned using the IVRS/IWRS. This number will be used to identify the subject throughout the clinical study and must be used on all study documentation related to that subject.

The subject identification number must remain constant throughout the entire clinical study; it must not be changed after initial assignment, including if a subject is rescreened.

6.5 Screen Failures

Screen failures are defined as subjects who consent to participate in the clinical study but are not subsequently enrolled in the study. A minimal set of screen failure information will be collected in the source documents that includes demography, screen failure details, eligibility criteria, and any serious adverse events.

Individuals who do not meet the criteria for participation in this study (screen failure) may be rescreened (Section [9.1.1](#)).

7. Treatments

Study treatment is defined as any investigational product(s), non-investigational product(s), placebo, or medical device(s) intended to be administered to a study subject according to the study protocol.

Note that in several countries, investigational product and non-investigational product are referred to as investigational medicinal product and non-investigational medicinal product, respectively.

Efavaleukin alfa will be manufactured and packaged by Amgen Inc. and distributed using Amgen clinical study drug distribution procedures. It is a liquid formulation presented in glass vials. An Investigational Product Instruction Manual (IPIM), containing detailed information regarding the storage, formulation, preparation, and administration of investigational product will be provided separately.

7.1 Treatment Procedures

7.1.1 Investigational Products

Table 7-1. Study Treatments

Study Treatment Name	Amgen Investigational Product: Efavaleukin Alfa
Dosage Formulation	Efavaleukin alfa is a liquid formulation presented in glass vials
Unit Dose Strength(s)/ Dosage Level(s) and Dosage Frequency	Phase 1b Cohort 1: [REDACTED] µg biweekly Cohort 2: [REDACTED] µg weekly Cohort 3: [REDACTED] µg biweekly Cohort 4: [REDACTED] µg weekly Cohort 5: [REDACTED] µg biweekly [REDACTED]
Route of Administration	Subcutaneous injection
Accountability	The amount of investigational product used in preparation, total volume of preparation, quantity administered, start date, start time, frequency, and lot number of efavaleukin alfa are to be recorded on each subject's CRF.
Dosing Instructions	A qualified staff member at the site will administer all SC injections in the abdomen, upper arm or thigh. A physician must be available at the time of administration of efavaleukin alfa Phase 1b: Subjects will receive weekly or biweekly SC doses of efavaleukin alfa at the site administered by study personnel for the duration of the study. Subjects will remain at the site for at least 1 hour following the first and second dose of efavaleukin alfa and for 30 minutes following all remaining doses. [REDACTED]

7.1.2 Non-investigational Products

Non-investigational products will not be used in this study.

7.1.3 Medical Devices

No investigational medical devices will be used in this study

Other non-investigational medical devices may be used in the conduct of this study as part of standard care.

Non-investigational medical devices (eg, syringes, sterile needles, and vials required for investigational product dilution) will be provided by Amgen. These items will be listed specifically in the IPIM.

7.1.4 Other Protocol-required Therapies

There are no other protocol-required therapies.

7.1.5 Other Treatment Procedures

There are no other treatment procedures in this study.

7.1.6 Product Complaints

A product complaint is any written, electronic or oral communication that alleges deficiencies related to the identity, quality, durability, reliability, safety, effectiveness, or performance of a drug, **combination product**, or device after it is released for distribution to market or clinic by either (1) Amgen or (2) distributors or partners for whom Amgen manufactures the material. **This includes all components distributed with the drug, such as packaging drug containers, delivery systems, labeling, and inserts.**

This includes any drug(s), device(s) or combination product(s) provisioned and/or repackaged/modified by Amgen. Drug(s) or device(s) includes investigational product. For this study, Amgen will collect product complaints for efavaleukin alfa.

Any product complaint(s) associated with an investigational product(s), non-investigational product(s), device(s), or combination product(s) supplied by Amgen are to be reported according to the instructions provided in the IPIM.

7.1.7 Excluded Treatments, Medical Devices, and/or Procedures During Study Period

Subjects may not initiate treatment with donor lymphocyte infusions, ECP, recombinant IL-2 (eg, aldesleukin, ILTOO), with T-cell depleting (eg, ATG, alemtuzumab), IL-2 signaling targeted medication (eg, basiliximab, daclizumab, denileukin diftitox) or Treg

cell expanding therapies (ie, recombinant IL-2, adoptively transferred Treg cells) during study participation.

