7.4.2.1.1 Phase 1b

Dose adjustment of efavaleukin alfa for individual subjects is not allowed until the [REDACTED] is determined. The Medical Monitor should be informed of withholding of efavaleukin alfa for acute clinical events such as acute infection or major surgery. Once the [REDACTED] dose is determined, all phase 1b subjects may continue study therapy at the [REDACTED] dose and frequency (at the discretion of the Sponsor, following discussion and agreement between the principal investigator and medical monitor) and will be subject to the dose adjustment guidelines in Section 7.4.2.1.2. A subject experiencing worsening of cGVHD that requires the addition of new immunosuppressive medication(s) at any time during the study or initiation of an increase in systemic corticosteroid dose above baseline after week 4 of the study (at the discretion of the treating investigator) will be deemed a treatment failure. These subjects will discontinue treatment and will have a safety follow-up visit (see Section 9.1.5).

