7.8 Prior and Concomitant Treatment

Throughout the study, investigators may prescribe any concomitant medications or treatments deemed necessary to provide adequate supportive care except for those listed in Section 7.1.7.

All other therapies including steroids, other immunosuppressive medications, prophylactic therapies for infections, and other medications considered supportive care for GVHD will not be provided or reimbursed by Amgen (except if required by local regulation). The investigator will be responsible for obtaining these therapies.

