7.8.2 Concomitant Treatment

Concomitant therapies are to be collected from first dose of investigational product through safety follow-up in the source documents and the eCRF.

For all therapies, collect therapy name, indication, dose, unit, frequency, route, start date, and stop date.

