7.8.2.1 Corticosteroids

7.8.2.2 Other Immunosuppressive Medications

Subjects will continue other systemic immunosuppressive background therapies (eg, tacrolimus, sirolimus, MMF, ECP) concomitantly with efavaleukin alfa. Addition or substitution of systemic immunosuppressive therapies beyond dose adjustments to maintain therapeutic levels will be considered a treatment failure. Dose reductions in background therapy are not allowed in the first 8 weeks of the study but may be reduced thereafter in responders at the discretion of the investigator. Disease flares during immunosuppressant taper will not be counted as GVHD progression or treatment failure if the subject can be managed by return to the baseline immunosuppressant dose. Topical immunosuppressant (ie, mouthwash, eye drops, genitourinary ointments) are allowed at the discretion of the investigator.

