8.1 Discontinuation of Study Treatment

Subjects can decline to continue receiving investigational product and/or other protocol-required therapies or procedures at any time during the study but continue participation in the study. If this occurs, the investigator is to discuss with the subject the appropriate processes for discontinuation from investigational product or other protocol-required therapies and must discuss with the subject the possibilities for continuation of the Schedule of Activities (see [Table 2-1](#), [Table 2-2](#), [Table 2-3](#), [Table 2-4](#), [Table 2-5](#), [Table 2-6](#), [Table 2-7](#), and [Table 2-8](#)) including different options of follow-up (eg, in person, by phone/mail, through family/friends, in correspondence/communication with other treating physicians, from the review of medical records) and collection of data, including endpoints, adverse events, and disease-related events, as applicable and must document this decision in the subject's medical records. Subjects who have discontinued investigational product and/or other protocol-required therapies or procedures should not be automatically removed from the study. Whenever safe and feasible, it is imperative that subjects remain on-study to ensure safety surveillance and/or collection of outcome data.

Subjects may be eligible for continued treatment with Amgen investigational product(s) and/or other protocol-required therapies by a separate protocol or as provided for by the local country's regulatory mechanism, based on parameters consistent with [Appendix 3](#).

Reasons for removal from protocol-required investigational product(s) or procedural assessments include any of the following:

- Decision by Sponsor
- Lost to follow-up
- Death
- Ineligibility determined
- Protocol deviation
- Non-compliance
- Adverse event
- Subject request
- cGVHD progression
- Requirement for alternative therapy
- Protocol-specified reasons as described in Section [7.4.1.2](#) and Section [7.4.2.1.2](#)
- Pregnancy

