9.2.5 Pharmacokinetic Assessments

9.2.6 Pharmacodynamic Assessments

Lymphocyte Subsets: Blood samples will be collected for all subjects at the time points indicated in the Schedule of Activities. These samples will be used to evaluate Treg, Tcon, and NK cells. Sampling time points for lymphocyte subsets may be modified based on emerging data.

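### PUVA and UVB are washed out at entry as Treg-expanding therapies but are not named in the on-study prohibition of that class (Protocol 7.1.7)

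*Protocol*

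**What the plan says.** **At entry.** Protocol 6.2, exclusion 204, keeps out anyone who has had "T regulatory cell expanding therapies (ie, PUVA, UVB, adoptively transferred T regulatory cells) within 4 weeks prior to starting efavaleukin alfa".

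**On study.** Protocol 7.1.7 lists what subjects may not start. It names donor lymphocyte infusion and ECP, so it is not confined to drugs. For the Treg-expanding class it reads "cell expanding therapies (ie, recombinant IL-2, adoptively transferred Treg cells) during study participation". PUVA and UVB do not appear.

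**Default for everything else.** Protocol 7.8 says that "investigators may prescribe any concomitant medications or treatments deemed necessary to provide adequate supportive care except for those listed in Section 7.1.7".

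**Rules that might catch phototherapy indirectly.** Section 7.4.2.1.1 makes a subject a treatment failure, who then stops product, if worsening cGVHD "requires the addition of new immunosuppressive medication(s) at any time during the study". Section 7.8.2.2 states: "Addition or substitution of systemic immunosuppressive therapies beyond dose adjustments to maintain therapeutic levels will be considered a treatment failure". Section 8.1 gives "Requirement for alternative therapy" as a reason for removal from product. None of the three mentions phototherapy.

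**What is measured.** Lymphocyte subsets are sampled in all subjects, and Protocol 9.2.6 says "These samples will be used to evaluate Treg, Tcon, and NK cells". Protocol 10.4.2.4.2 summarizes PD by dose level; the parameter names there are redacted.

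**The concern.** The entry washout only makes sense if the sponsor thinks PUVA and UVB can change Treg levels. The same reasoning applies after the first dose, yet the on-study list leaves them out, and 7.8 makes that list the reference for what is barred. One site could stop efavaleukin alfa when a subject starts phototherapy. Another could treat it as supportive skin care and continue dosing.

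In the second case, later Treg values would enter the summary for that subject's dose. The study has no control arm and SAP 4.1 plans no covariates, so the tables could not separate a phototherapy effect from a drug effect.

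**Working it through.** The plan gives no figure on this point, so there is none to reproduce. The check compares the texts and then scales a possible effect.

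**Step 1. The two lists.**

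| Therapy | Exclusion 204 (Treg-expanding, 4-week washout) | 7.1.7 (Treg-expanding, may not be started) |
|---|---|---|
| Adoptively transferred Tregs | named | named |
| PUVA | named | not named |
| UVB | named | not named |
| Recombinant IL-2 | not named here (IL-2 is in 203, 12 weeks) | named |

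Both lists are fully readable, so the mismatch is not a redaction effect.

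**Step 2. Does another rule close the gap?** Section 7.8.2.2 gives ECP, a procedure, as an example of systemic immunosuppressive background therapy, so that rule reaches beyond drugs. PUVA is psoralen plus ultraviolet A (Appendix 1) and so includes a drug. PUVA started for worsening cGVHD therefore probably counts as treatment failure. UVB alone involves no drug and is the least clearly covered. Phototherapy given as skin care, without a declared worsening, is not clearly caught by any of the three rules.

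**Step 3. Which samples would be affected?** If product stops, SAP 9.7.1.2 drops end-of-treatment PD samples taken more than 9 days (QW) or 16 days (Q2W) after the last dose, and samples after skipped doses. What remains is a subject who starts phototherapy, keeps dosing and keeps giving samples. The readable part of SAP 9.7.1.2 has no rule for those. Protocol 7.8.2.1 and 7.4.2.1.2 and parts of the PD text are not readable, so a rule there cannot be ruled out.

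**Step 4. Scale, on assumed effects.** Inputs:
- Geometric-mean summaries (SAP 9.7.1.2).
- Cohort size n = 6, the planned size for cohorts 3 to 5, with a design minimum of 3 (Protocol 5.1.1).
- A phototherapy effect f on Tregs of 1.25, 1.5 or 2. These values are assumptions; the documents give none.
- A yardstick of roughly 30%, the predicted step between two Q2W doses (Protocol 5.4). The measure is redacted; taking it as a Treg measure is an assumption from the paragraph's subject.

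If m of n subjects are affected, the cohort geometric mean is multiplied by f^(m/n). The share of the yardstick on the log scale is (m/n) × ln f / ln 1.3.

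| f | 1 of 6: f^(1/6) − 1 | Share of 30% step | 1 of 3: f^(1/3) − 1 |
|---|---|---|---|
| 1 (no effect) | 0% | 0% | 0% |
| 1.25 | 3.8% | 14% | 7.7% |
| 1.5 | 7.0% | 26% | 14.5% |
| 2 | 12.2% | 44% | 26.0% |

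To match the whole 30% step, one subject in six would need a 1.3^6 = 4.8-fold effect; two in six would each need 1.3^3 = 2.2-fold.

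**The case against.** The strongest reply is that phototherapy is already barred by class. Section 7.1.7 prohibits Treg-expanding therapies, and the protocol itself puts PUVA and UVB in that class. A reader might infer from the *ie* in 7.1.7 that its list is exhaustive and that phototherapy is therefore allowed. The documents do not support that. Sections 7.8.2.2 and 7.8.2.3 use *ie* to introduce what are plainly examples (topical agents, anti-infective prophylaxis). The two Treg lists also cannot both be complete, since each names something the other lacks. Further, 7.8 frees only supportive care, and the one thing the protocol says about PUVA and UVB is that they expand Tregs. Together with the failure rules, this makes the gap narrow, and that part of the reply stands.

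It does not remove the gap. The class reading requires a site to carry a definition from an entry criterion into a separate list that names different members. The supportive therapies in 7.8.2.4 are also explicitly open-ended.

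A second reply is that SAP 8.4 and 9.3 review important protocol deviations and SAP 9.6.9 summarizes therapies of interest. These could bring cases to light. But phototherapy is a deviation only if it is barred, which is the open question, and none of these sections removes or marks a PD sample.

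A third reply is that the yardstick is weak. It appears to concern the added cohort 5 dose. SAP 3.1 reports that enrollment at that dose was discontinued and ongoing subjects were dose-reduced, so a full cohort of six may not exist there. That is fair; the yardstick serves only as a sense of scale.

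**Conclusion.** The point holds as a minor one. Entry and on-study wording for the same class do not match, and the text leaves open that a subject starts phototherapy, UVB especially, while staying on product and in the PD summaries.

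The size is unknown and may be zero. The percentages above rest entirely on assumed fold effects, and that Tregs are among the by-dose parameters is inferred from Protocol 9.2.6. Protocol 5.4 reports high inter-subject variability, so a shift from one subject would be hard to see.

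A reader might go further and infer that the by-dose Treg results are confounded, or that clinical response is flattered too. The documents support neither: they record no on-study phototherapy and state no effect of it on Tregs or on response.

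The reach is limited to descriptive PD. The primary endpoints are DLTs and adverse events (SAP 2.1), no statistical hypothesis is planned (SAP 2.2), no secondary endpoint is an efficacy endpoint (SAP 9.5.2), and the expansion cohort and phase 2 are cancelled (SAP 3.1).

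**What to change.** 1. **Protocol 7.1.7:** add PUVA and UVB to the Treg-expanding therapies so that the list matches exclusion 204. This is one phrase. Because the study is ending early, it protects only subjects still on treatment.
2. **SAP 9.7.1.2:** flag and list PD samples taken after any on-study PUVA or UVB exposure, and repeat the by-dose PD summary without them as a sensitivity analysis. Affected subjects can be found from data already gathered, since Protocol 7.8.2 instructs: "For all therapies, collect therapy name, indication, dose, unit, frequency, route, start date, and stop date".

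The main summary should keep these samples. Phototherapy is likely to follow the course of disease, so dropping everything after first exposure could introduce a selection of its own. The cost is one or two SAP sentences and one extra table, with no new data collection. If nobody received phototherapy, one line saying so is enough.
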